#### 4.7 Justification of target sample size

The target sample size currently assumes an attrition rate of 10% at two years after index surgery. In practice, the power of the study will be increased by follow-up longer than two years for a proportion of participants and decreased by follow-up shorter than two years for a proportion (e.g. due to mortality, participants requesting to withdraw, or planned closures of loop ileostomies). These factors will be monitored as data accrues for the study, their consequences for the target sample size will be modelled and the target sample size revised if appropriate.

We have estimated the hazard ratio that the study will be able to detect for a range of scenarios. The incidence of PSH is unknown; we have considered incidences of 30% and 40% as plausible. Surgical methods of interest are used with varying frequencies and so we have considered the impact of a range of ratios for the use of technical variation when comparing one variation with another, i.e. ratios of 1:1, 1:2, 1:5, 1:10 and 1:20. The correlation of the exposure of interest with other covariates is also unknown and we considered the impact of a range of correlations (0, 0.3 and 0.5). The hazard ratios that can be detected from a study of 4000 participants at the 5% level (2-sided) are shown in **Table 3**. For simplicity, we have assumed a binary exposure variable. For multi-category exposures, we will assess the overall effect of the exposure; if we were to adjust the significance level from 5% to 2% to allow for comparisons between subcategories, the power reduces from 90% (80%) to 82% (68%).

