# Table 3:Hazard ratios detectable in the CIPHER study for a range of assumptions,
based on a cohort of 4,000 participants.

Ratio of presence:	Squared correlation	Incidence of	Hazard ratio	o detectable
absence of covariate	with other covariates	PSH	90% power	80% power
1:1	0 (i.e. unadjusted)	40%	1.18	1.15
	0.3		1.21	1.18
	0.5		1.26	1.22
	0 (i.e. unadjusted)	30%	1.21	1.18
	0.3		1.25	1.21
	0.5	1.30		1.26
1:2	0 (i.e. unadjusted)	40%	1.19	1.16
	0.3		1.23	1.19
	0.5		1.28	1.23
	0 (i.e. unadjusted)	30%	1.22	1.19
	0.3		1.27	1.23
	0.5		1.32	1.27
1:5	0 (i.e. unadjusted)	40%	1.24	1.21
	0.3		1.30	1.25
	0.5		1.36	1.30
	0 (i.e. unadjusted)	30%	1.29	1.24
	0.3	1.35		1.30
	0.5	1.43		1.36
1:10	0 (i.e. unadjusted)	40%	1.33	1.28
	0.3		1.40	1.34
	0.5		1.49	1.41
	0 (i.e. unadjusted)	30%	1.39	1.33
	0.3		1.48	1.40
	0.5	1.59		1.49
1:20	0 (i.e. unadjusted)	40%	1.46	1.39
	0.3		1.58	1.48
	0.5		1.71	1.59
	0 (i.e. unadjusted)	30% 1.55		1.46
	0.3		1.69	1.57
	0.5		1.86	1.71

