## 5.2 Research procedures

Patients will undergo stoma formation in accordance with the techniques habitually used by each participating surgeon. The details of the procedure and aftercare will be at the discretion of the surgeon and in accordance with usual practice at each participating centre.

Research procedures for the purposes of the study only include:

- Provision of study information, review of the eligibility criteria and invitation to eligible patients to consent;
- Collection of key baseline, intraoperative and post-operative data for participants;
- Completion by participants of follow-up questionnaires, at the intervals specified in Table 3;
- Requests for participants' CT scans carried out in the course of usual care during the follow-up period.

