#### 8. Statistical analyses

#### 8.1 Plan of analysis

The data will be analysed according to the intention to implement a surgical step and will be reported in accordance with the principles of the CONSORT guidelines (but not items relating to randomization). A detailed statistical analysis plan will be prepared prior to locking the database. The primary outcome, time to PSH (defined as the time when PSH confirmed by imaging) and secondary time-to-event outcomes, will be analysed using survival methods. The models will take account of the hierarchical structure of the data; i.e. participants, nested within surgeons nested within centres. The hazards of key predictors will be estimated, with 95% confidence intervals, after adjusting for important procedure, patient and surgeon confounding factors.

Exploratory analyses will be used to inform the choice of survival distribution (e.g. Weibull). The factors included in the model, the modelling strategy and the approach to handling correlated covariates will be documented in the statistical analysis plan. Participants free from a PSH at final follow-up will be censored. Follow-up will also be censored if bowel continuity is restored, if participants have a redo stoma or die. These circumstances leading to censoring may be informative and sensitivity analyses (setting survival times to the longest observed times) will be undertaken to assess the potential impact of informative censoring. Secondary continuous outcomes will be analysed using a mixed regression models, again taking account of the hierarchical structure of the data and the repeated measurements over time. Binary outcomes (e.g. complications) will be analysed using

logistic regression. If the frequency of the outcomes allows, these models will also take account of the hierarchical structure of the data.

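### Table 3 assumes 4,000 independent participants, so its 90% and 80% power is overstated for techniques that vary mainly between surgeons, the hierarchy that the planned model includes

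*Protocol*

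**What the plan says.** Section 4.7 introduces the power statement with "The hazard ratios that can be detected from a study of 4000 participants at the 5% level (2-sided) are shown in" Table 3, and assumes a binary exposure. On the event proportion it says "we have considered incidences of 30% and 40% as plausible". For the split between technique variants it uses "ratios of 1:1, 1:2, 1:5, 1:10 and 1:20". It also varies the correlation of the exposure with other covariates (0, 0.3 and 0.5, headed in Table 3 as squared correlation). The title of Table 3 describes the results as "based on a cohort of 4,000 participants". The section mentions no ICC, design effect, number of surgeons or patients per surgeon.

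Section 8.1 says of the survival analyses: "The models will take account of the hierarchical structure of the data; i.e. participants, nested within surgeons nested within centres".

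Section 5.2 says how the exposure arises: "Patients will undergo stoma formation in accordance with the techniques habitually used by each participating surgeon". Section 4.8(i) describes two extremes: (a) a surgeon applies one preferred variant to all patients, or (b) a surgeon uses several variants and chooses by patient characteristics or other factors. It leaves open which applies and says the accruing surgical data will show it. Section 5.7 repeats that these data will be inspected.

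**The concern.** The power is stated for one model and the analysis is committed to another. If patients of the same surgeon share part of their hernia risk, and a technique is used by some surgeons and not by others, the comparison of techniques is partly a comparison of surgeons. Each extra patient of the same surgeon then adds less information than an independent patient would. The hierarchical model in section 8.1 reflects this in wider intervals; Table 3 does not.

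At stake is the reading of a null result. A reader who takes Table 3 at face value could conclude that the cohort had 90% power for a given hazard ratio when, for a surgeon-level technique, it had less. No stated safeguard would bring this to light. The factors that section 4.7 will monitor for revising the sample size concern length of follow-up (longer follow-up, death, withdrawal, stoma closure), and section 5.10 adds a review of attrition from death. Clustering is in neither.

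**Working it through.** **Step 1: reproduce Table 3.** Inputs from section 4.7: N = 4,000; incidence 30% or 40% (1,200 or 1,600 events); exposure ratio 1:k, so p = 1/(1+k); R² = 0, 0.3 or 0.5; two-sided 5%. The Schoenfeld formula with a covariate term is

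HR = exp[(1.960 + z) / √(N × incidence × p(1−p) × (1−R²))], with z = 1.2816 for 90% power and 0.8416 for 80%.

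For the row 1:10, 30%, R² = 0.3: p = 1/11, and 4,000 × 0.3 × (1/11)(10/11) × 0.7 = 69.42. Its square root is 8.332, and 3.2415/8.332 = 0.389. Then exp(0.389) = 1.48, as tabulated. Over the whole table, 57 of the 60 hazard ratios match to two decimals and the other 3 differ by 0.01. The table's arithmetic is right for independent participants, and the formula leaves no room for a clustering term.

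**Step 2: add the surgeon level.** For an exposure constant within surgeon, with about m patients per surgeon, the variance of the log hazard ratio is multiplied by approximately

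DE = 1 + (m−1) × ICC.

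Power at the tabulated hazard ratio becomes Φ[(1.960 + z)/√DE − 1.960]. The detectable hazard ratio becomes exp(ln HR × √DE).

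Neither m nor the ICC is in the protocol, so both are assumptions, shown as a range. The formula assumes similar numbers of patients per surgeon and is an approximation for a censored time-to-event outcome.

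| Patients per surgeon (m) | ICC | DE | Nominal 90% becomes | Nominal 80% becomes |
|---|---|---|---|---|
| 5 | 0.01 | 1.04 | 88.9% | 78.4% |
| 5 | 0.05 | 1.20 | 84.1% | 72.5% |
| 10 | 0.02 | 1.18 | 84.7% | 73.2% |
| 10 | 0.05 | 1.45 | 76.8% | 64.3% |
| 20 | 0.05 | 1.95 | 64.1% | 51.8% |

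Worked line for DE = 1.45: √1.45 = 1.204; 3.2415/1.204 = 2.692; 2.692 − 1.960 = 0.732; Φ(0.732) = 76.8%.

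**Step 3: detectable hazard ratios at 90% power with DE = 1.45.**

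| Row of Table 3 | Tabulated | With DE 1.45 |
|---|---|---|
| 1:1, 40%, R² = 0 | 1.18 | 1.22 |
| 1:10, 30%, R² = 0.3 | 1.48 | 1.60 |
| 1:20, 30%, R² = 0.5 | 1.86 | 2.11 |

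**Step 4: does the R² column already cover this?** Section 4.7 defines it as correlation of the exposure with other covariates. The design effect comes from outcome risk shared by a surgeon's patients, which is a different quantity, and the two inflations can combine. In the last row above, R² = 0.5 multiplies the variance by 2 and DE by 1.45, so by 2.9 in all.

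**Step 5: exposure that varies within surgeon.** If each surgeon uses both variants, part or all of the comparison is made within surgeon and DE falls towards 1. Table 3 is then close to right.

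**The case against.** The strongest reply is that the protocol does not say technique is constant within surgeon. Section 4.8(i) leaves (a) and (b) open, and section 5.2 leaves details of the procedure to the surgeon's discretion, which fits (b) too. Some exposures, such as stoma type, are plausibly driven by the patient's condition. This stands: a reader might infer that Table 3 is wrong for every exposure, and the protocol does not support that.

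The size is also assumed. At an ICC of 0.01 and 5 patients per surgeon, the loss is one to two points. This stands as well, but it is no reason to leave the input out. Section 4.7 also calls the incidence and the covariate correlation unknown, and tabulates both over a range.

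The table is a sensitivity grid, and R² = 0.5 already doubles the variance, which exceeds the largest design effect used here (1.95). That shows the grid spans inflation of a similar size. It does not show that clustering is allowed for, because that column is already taken up by the covariates.

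Finally, the reported 95% confidence intervals will come from the hierarchical model and will show the real precision. That limits the harm to the reading of the power statement.

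Two further inferences go too far. One is that technique is uniform across a whole trust, which would give far larger losses; sections 4.8(i) and 5.2 speak only of surgeons. The other is that the table is miscalculated, which Step 1 rules out.

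**Conclusion.** The point holds conditionally. Table 3 rests on an unstated assumption of independent participants, which does not match the model in section 8.1. For techniques that vary mainly between surgeons, the stated power is overstated: 90% becomes about 89% down to 64%, and 80% about 78% down to 52%. These ranges rest on 5 to 20 patients per surgeon, an ICC of 0.01 to 0.05 and exposure constant within surgeon, none of which can be checked from the protocol.

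For scale, section 4.7 thought it worth reporting that a 2% significance level lowers power from 90% to 82% and from 80% to 68%. A design effect of 1.20 takes 90% to 84.1% and 80% to 72.5%, and goes unmentioned. None of this shows that 4,000 is the wrong target.

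**What to change.** Keep the target of 4,000. In section 4.7, state that Table 3 assumes independent participants and applies only to techniques that vary within surgeon.

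For surgeon-level techniques, restate the detectable hazard ratios by multiplying ln(HR) by √[1 + (m−1) × ICC], over a stated range of ICC and patients per surgeon. Update m, and the extent to which each technique varies within surgeon, from the accruing surgical data that sections 4.8(i) and 5.7 already plan to inspect. Add clustering to the factors monitored in section 4.7.

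The cost is a few sentences and a supplementary set of rows. The downside is that the stated detectable hazard ratios become less favourable.

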#### 3. Aims and objectives

The CIPHER study (Phase B; CIPHER-B) aims to establish the incidence of symptomatic and radiologically confirmed PSH during a minimum of 2 years follow up. Additionally, CIPHER aims to evaluate the effects of key technical surgical steps during index stoma formation on the risk of subsequent PSH formation.

Specific objectives of CIPHER-B are:

- 1. To describe the incidence of PSH formation within 2 years of formation of all types of stomata other than loop ileostomies;
- 2. To describe the risk of PSH for different types of stoma (end colostomy versus loop colostomy versus end ileostomy)
- 3. To describe the risk of PSH according to how the stoma trephine is created in the anterior fascia of the abdominal wall with respect to location (within or without the rectus sheath) and shape (cross versus circle versus slit);
- 4. To describe the relative risk of PSH following index stoma creation with or without mesh (no prophylactic mesh versus biologic mesh versus synthetic mesh);
- To describe the relative risk of PSH following index stoma creation with prophylactic mesh according to mesh position (intra-abdominal versus sublay/retrorectus versus. onlay);
- 6. To describe the relative risk of PSH with different trephine shapes in the mesh (circle versus cross versus slit versus none (Sugarbaker)).
- 7. To estimate the cost effectiveness of commonly used types of mesh (e.g. biologic, synthetic) versus no prophylactic mesh in prevention PSH and improving health related quality of life.

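### The power quoted in Protocol section 4.7 for comparisons between subcategories lowers only the significance level and still counts all 4,000 participants, so it is too high for a pair drawn from three or more categories

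*Protocol*

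**What the plan says.** Protocol section 4.7 rests on a two-group calculation: "The hazard ratios that can be detected from a study of 4000 participants at the 5% level (2-sided) are shown in" Table 3, and "For simplicity, we have assumed a binary exposure variable". It introduces the ratios 1:1 to 1:20 as those that arise when one technical variation is compared with another. For exposures with several categories it says that the overall effect will be assessed, and then gives a figure for the pairwise case: "if we were to adjust the significance level from 5% to 2% to allow for comparisons between subcategories, the power reduces from 90% (80%) to" lower figures, printed as 82% (68%).

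Section 3 sets several comparisons with more than two categories:

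- Objective 2: "To describe the risk of PSH for different types of stoma (end colostomy versus loop colostomy versus end ileostomy".
- Objective 3: trephine location (two levels) and "shape (cross versus circle versus slit".
- Objective 4: no mesh, biologic mesh or synthetic mesh.
- Objective 5: three mesh positions, among participants with prophylactic mesh.
- Objective 6: four options for the trephine in the mesh, one of them being no trephine.

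**The concern.** Comparing subcategories costs power in two ways. The significance level is tightened for multiplicity, and each contrast uses fewer participants because those in the remaining categories carry no information about it. Section 4.7 charges for the first and not the second.

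Apart from trephine location, every categorical exposure in objectives 2 to 6 has three or four levels, so the remaining categories will seldom be empty. For stoma type there is also a likely fourth group. Objective 2 lists three types without loop ileostomy, yet section 4.4.2 does not exclude loop ileostomies and section 4.7 expects some of them to be closed.

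A reader of 4.7 would take an inconclusive comparison of, say, two trephine shapes as coming from a study with 82% power at the Table 3 hazard ratio. Section 4.7 also promises to model and revise the target sample size as data accrue, and that exercise needs a correct starting figure.

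**Working it through.** **Inputs.** From section 4.7 and Table 3: N = 4,000; two-sided alpha 5%, then 2%; power 90% (80%); incidence 40% or 30%, giving 1,600 or 1,200 events; a binary exposure. The share of participants in each category is not given and is assumed below. Attrition, clustering and incidence are left as in Table 3. Normal quantiles: z(0.975) = 1.960, z(0.99) = 2.326, z(0.90) = 1.282, z(0.80) = 0.842.

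**1. Table 3.** With p the proportion exposed and R² the squared correlation with other covariates,

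HR = exp{ [z(0.975) + z(power)] / √[N × incidence × (1 − R²) × p(1 − p)] }.

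With N = 4,000 this reproduces all 60 entries (largest difference 0.005). Example, 1:1, R² = 0, 40%, 90% power: exp(3.2415/√400) = 1.176, printed as 1.18.

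**2. The printed 82% (68%).** Keep the same signal and change alpha only:

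- Φ(1.960 + 1.282 − 2.326) = 0.820
- Φ(1.960 + 0.842 − 2.326) = 0.683

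Both printed figures are recovered. A one-sided 2% level gives 0.883 (0.773) and alpha = 5%/3 gives 0.802 (0.658); neither matches. So only alpha was changed, and the full cohort stayed in two groups.

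**3. A pair of categories.** For categories A and B holding fractions a and b of the cohort, the information on their log hazard ratio is D × ab/(a + b), where D is the total number of events. Put s = a + b and q = a/s. This equals D × s × q(1 − q): the two-group information for the same A:B ratio, multiplied by s. At the Table 3 hazard ratio for that ratio,

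power at 2% = Φ{ [1.960 + z(power)] × √s − 2.326 }.

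The hazard ratio detectable with 90% power at 5%, for a 1:1 pair with R² = 0, is exp{3.2415/√(D × s/4)}.

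| Share s in the pair (assumed) | Power at 2%, base 90% (80%) | Detectable HR, 40% incidence | Detectable HR, 30% incidence |
|---|---|---|---|
| 1 (as printed) | 82.0% (68.3%) | 1.18 | 1.21 |
| 0.9 | 77.3% (63.0%) | 1.19 | 1.22 |
| 2/3 (three equal categories) | 62.6% (48.4%) | 1.22 | 1.26 |
| 1/2 (four equal categories) | 48.6% (36.5%) | 1.26 | 1.30 |

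Using Table 3's rounded 1.18 in place of 1.176 (40% incidence) gives 83.7% with all 1,600 events and 64.7% with two-thirds of them, so rounding does not explain the gap.

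**4. Unequal categories.** Each pair is taken at the Table 3 hazard ratio for its own ratio, base power 90%:

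- 45/45/10: 77.3%, 53.1%, 53.1%
- 50/25/25: 68.5%, 68.5%, 48.6%
- 80/10/10: 77.3%, 77.3%, 19.0%

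Against 82.0%, a single pair loses from about 5 points (82.0 − 77.3) to 63 points (82.0 − 19.0).

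**5. Mesh users only.** For objectives 5 and 6, if a fraction m of the cohort has mesh, s becomes m times the pair's share among mesh users. Any m below 1 takes power below the corresponding table row.

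**6. The overall test.** For three equal categories the test has 2 degrees of freedom and noncentrality D × the variance of the log hazard ratios across categories. At the 1:1 hazard ratio, D × (log HR)² = 4 × 3.2415² = 42.0 for base 90% and 4 × 2.8016² = 31.4 for base 80%.

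- One category differs (variance 2/9 of the squared log HR): noncentrality 9.34 (6.98), power at 5% 79% (65%).
- Evenly spaced effects (variance 1/6): noncentrality 7.01 (5.23), power 66% (52%).

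**The case against.** The best defence is that the alpha shift is right at every row of Table 3, provided the right row is chosen. A three-level exposure enters a Cox model as two indicators. With equal thirds, each has a presence:absence ratio of 1:2 and squared correlation 0.25 with the other, so the information is N × incidence × (2/9) × 0.75 = N × incidence/6. That is identical to step 3 with s = 2/3. The detectable hazard ratios are then 1.22 and 1.26, between the printed 1:2 rows, and at those values power at 2% is indeed 82%. The figures are also right for one category against all the others combined. This algebra stands, so a reader who inferred that the printed powers hold only when all other categories are empty would go too far. But section 4.7 describes the ratio as that between two variations being compared, and treats the correlation as one with other covariates. Nothing in it leads a reader to the row that would make the sentence correct.

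Second, the binary simplification is disclosed, the alpha adjustment is conditional, the objectives are phrased as descriptions, and many steps in Table 1 are yes/no items for which the formula is apt. All true. But the disclosure covers Table 3, and the sentence at issue goes on to give numbers for the non-binary case.

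Third, section 8.1 promises 95% confidence intervals, so a null pairwise result would be read from its interval. That limits the harm and does not correct the stated power.

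**Conclusion.** The point stands as an error in a stated power. The 82% (68%) offered for comparisons between subcategories accounts for the tighter alpha and leaves out the loss of events. When the Table 3 ratio is taken as the ratio between the two categories compared, the direction is certain: any non-empty further category lowers pairwise power below the printed value.

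The size is not certain. It rests on category shares that the Protocol does not give, with attrition, clustering and incidence kept as in Table 3. A reader might infer a general overstatement of about 20 points, or a true power of 63%. The documents do not support either as a fixed figure: both belong to three equal categories, and single-pair losses in the splits tried run from about 5 to 63 points.

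Nor does the Protocol claim 90% (80%) for the overall multi-category test; it says only that the overall effect will be assessed. The fair criticism is that 4.7 gives no power for that test and that the binary figures would not apply to it.

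The practical effect is on how the study's sensitivity is described. On the hazard ratio scale, equal thirds move the 1:1 entries from 1.18 to 1.22 (40% incidence) and from 1.21 to 1.26 (30%). Design and recruitment are not affected.

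**What to change.** Replace the last sentence of section 4.7 with text to this effect:

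> For a comparison between two categories of a multi-category exposure, power depends on the events in those two categories. At the Table 3 hazard ratio for the ratio between them, and at a 2% level, power is 77% (63%) if the pair holds 90% of the cohort, 63% (48%) if it holds two-thirds and 49% (37%) if it holds half. These shares are assumptions. For mesh position and the trephine in the mesh, the share is counted among all participants, so power is lower. The powers in Table 3 are for a binary exposure and do not carry over to the overall test with k − 1 degrees of freedom; for three equal categories that test has about 66% to 79% power where the binary figure is 90%, depending on the pattern of effects.

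Detectable hazard ratios for the same pair shares could be printed instead. Observed category shares can replace the assumed ones when the sample size is reviewed, as 4.7 already foresees.

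The cost is one rewritten passage or a few table rows. No extra patients are needed; the stated power becomes less favourable.
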